9.1 Study Design

This is a prospective, multi-country, multi-center observational study involving long-term follow-up of B-precursor ALL patients treated with either blinatumomab or SOC chemotherapy prior to alloHSCT. The study will have no effect on treatment practices of included patients due to its observational nature. The primary and secondary objectives relate to the description and comparison (pending adequate sample size is enrolled [≥ 50 patients per arm]) of the long-term safety profile of blinatumomab versus chemotherapy, prior to alloHSCT, in paediatric patients.

9.2 Setting and Study Population

Patients will be recruited from clinical sites from countries listed in Section 9.2.2. Amgen also plans to use the European Society for Blood and Marrow Transplantation (EBMT) Registry to leverage their network to identify potentially suitable sites which can be approached for study participation. Amgen intends to enroll paediatric patients that are treated with blinatumomab or SOC followed by alloHSCT.

9.2.1 Study Period

Enrolment of patients into 20180130 will occur if they meet all eligibility criteria. All eligible patients or their caregivers/legal guardians will be approached to provide informed consent for participation. Once informed consent has been given, and all inclusion/exclusion criteria are met, the patient will be enrolled via interactive response technology (IRT) in the study and data collection will begin. The study will commence at the first data collection of the first site. Patients will be followed for a maximum of a 12-year period or up to the age of 25 years, death, withdrawal of consent, or loss to follow-up, whichever comes first. The study will end when 12 years of follow-up for the last patient (if the patient has not withdrawn consent, been lost to follow-up, or died before the end of the 12 years of follow-up) is completed. If the last patient enrolled on study dies or is lost to follow-up before the 12 years following alloHSCT, the remainder

of the patients on study will continue to be followed until all patients on study have reached 12 years following alloHSCT, until death, withdrawal of consent, or lost to follow-up, whichever occurs first.

Data will be entered into an eCRF and will encompass information abstracted from patient charts from routine clinical visits. Data abstraction will be performed approximately every 6 months (± 30 days) starting at enrolment. Additional data on neuropsychomotor development will be assessed through specific questionnaires (paper and/or electronic) which will be administered at pre-specified intervals starting at enrolment (approximately every 6 months [± 30 days] for patients up to 6 years old and approximately yearly [± 60 days] for patients from 6 years old).

The first day of follow-up (day 1) will be the date of successful completion of alloHSCT (following chemotherapy/ blinatumomab treatment).

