9.2.5 Study Follow-up

This is a prospective study where data will be collected at routine clinical visits which will occur per standard of care (for a period of up to 12 years). A total of 12 years follow-up or 144 months of follow-up is planned for study 20180130. At each data collection stage, relevant information will be retrieved from patient charts subsequent to the preceding data abstraction time point to ensure there is no gap in data collection. Data abstraction will be performed approximately every 6 months (± 30 days) starting at enrolment. Additional data on neuropsychomotor development will be assessed through specific questionnaires (paper and/or electronic) which will be administered at pre-specified intervals starting from enrolment (approximately every 6 months [± 30 days] for patients up to 6 years old and approximately yearly [± 60 days] for patients from 6 years old). For each enrolled patient, data collection will end at 12-years of follow-up, the age of 25 years, loss-to-follow-up, withdrawal of consent, or death, whichever occurs earliest. All treatments for ALL will be captured in this period.

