9.5 Study Size

The targeted sample size for this study is approximately 298 patients. However, the actual number of patients that will be included in the study will depend on the results of site feasibility, willingness of patients (or their legal guardians/caregivers) or sites to participate in the study.

According to Marshall et al 2013, paediatric ALL patients are expected to have toxicity during intensification of therapy, generally related to hematological counts (Marshall et al, 2013). All patients also expect to have some immune complications after treatment end (Perkins et al, 2017) that will persist for some time.

Assuming that between 85%-98% of all patients will have at least one event, the expected ranges of sample sizes and relevant 95% CI is provided below. If 100 patients are enrolled.

95% C	onfidence	Interval o	of Estimated	Incidence o	of Adverse	Events by	Sample
-------	-----------	------------	--------------	-------------	------------	-----------	--------

S	ize	

Enrolled N Per Arm	Estimated Incidence of events	95% Confidence Interval*
150	98%	94.3%-99.3%
150	90%	84.1%-93.9%
150	85%	78.4%-89.8%
100	98%	93%-99.5%
100	90%	82.5%-94.5%
100	85%	76.7%-90.7%
75	98%	90.8%-99.3%
75	90%	82.0%-95.4%
75	85%	75.6%-91.6%
50	98%	89.5%-99.7%
50	90%	78.6%-95.7%
50	85%	71.5%-91.7%

* Wilson score interval

Sample size calculation for comparison analyses was calculated based on the number of long-term survivors needed. A risk difference of 10% (98% vs 88%) is considered as clinically significant. If the sample size is 52 long-term survivors per arm (104 in total), then a risk difference of as little as 10% will be detectable (p-value < 0.05).

Number of Long-term Survivors per Arm	Observed Risk Difference	P-value*
52/52	98% vs 88% = 10%	0.0455
40/40	98% vs 86% = 12%	0.0477
30/30	98% vs 83% = 15%	0.0477
20/20	98% vs 77% = 21%	0.0444

* z-test of two proportion comparison

Assuming a 35% long-term survival rate, the required number of patients entering the study per arm is 149 (52/0.35). Therefore, the number of patients entering the study needed to successfully fulfill the primary objectives while taking into account the 35% survival rate is 298.

Even though long-term survivors contribute the most essential data to this study, all enrolled patients contribute important information. If the total sample size is 149 patients per arm (298 in total), then a risk difference of as little as 5% will be detectable (p-value < 0.05).

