Enrolled N per Arm	Observed Risk Difference	P-value*
149/149	98% vs 95% = 5%	0.0375

* z-test of two proportion comparison

It will be attempted to recruit an approximately equal number of patients for each age group of long-term survivors (0-2 years, 3-6 years, 7-12 years, 13-17 years) to ensure that there will be enough data collected for each age group.

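### The 149-per-arm size allows only for death although follow-up has other exits, and the age-25 cap makes the follow-up behind the logistic comparison unequal

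*Protocol*

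**What the plan says.** Section 9.5 sizes the comparison on survivors: "If the sample size is 52 long-term survivors per arm (104 in total"), a difference of 98% vs 88% is said to be detectable at p < 0.05. It then states: "Assuming a 35% long-term survival rate, the required number of patients entering the study per arm is 149 (52/0.35"), which gives the target: "The targeted sample size for this study is approximately 298 patients". Survival is the only inflation factor. Neither the term long-term survivor nor the 35% rate carries a time point.

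Section 9.2.1 starts follow-up at the transplant and says: "Patients will be followed for a maximum of a 12-year period or up to the age of 25 years", with death, withdrawal of consent and loss to follow-up as further exits, whichever is first. Section 9.2.5 adds: "A total of 12 years follow-up or 144 months of follow-up is planned for study 20180130". Section 9.5 also aims at roughly equal recruitment "for each age group of long-term survivors (0-2 years, 3-6 years, 7-12 years, 13-17 years").

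Section 9.2.1, and the Follow-up paragraph of the Abstract, say that if the last patient enrolled dies or is lost before 12 years, the remaining patients "will continue to be followed until all patients on study have reached 12 years following alloHSCT", or until death, withdrawal or loss. Age 25 is not in that list.

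Section 9.7.2.2.3 compares incidence endpoints by logistic regression and time-to-event endpoints by Cox regression. Kaplan-Meier estimates of time to first onset are also planned.

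**The concern.** A size built as survivors divided by a survival rate is right only if death is the sole reason a patient fails to supply the data counted on. Here three more exits are written into the protocol, one of them fixed by age, and the calculation allows for none of them. At stake is whether the enrolled number supports the 10-point difference that the protocol calls clinically significant.

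The age exit also affects the analysis. Adolescents can be observed for up to five years less than younger children. A logistic model for whether an event was ever recorded treats these patients as if they had been watched equally long. If the age mix differs between blinatumomab and chemotherapy, unequal observation can pass for a treatment difference. If it does not differ, the proportions still refer to no definite time.

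**Working it through.** **Inputs.** From Section 9.5: 52 survivors per arm, 35% survival, 98% vs 88%, z-test of two proportions, four age bands. From Section 9.2.1: follow-up from transplant to 12 years or age 25. Loss to follow-up is not given; 10% to 30% is an assumption used to show a range.

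**1. Reproduce the plan.** 52 / 0.35 = 148.57, rounded up to 149; 2 x 149 = 298. For 98% vs 88% at 52 per arm with a two-sided pooled z-test, the mean proportion is 0.93, SE = sqrt(2 x 0.93 x 0.07 / 52) = 0.0500, z = 0.10 / 0.0500 = 2.00, p = 0.0457 (protocol: 0.0455). The 40, 30 and 20 per arm rows give 0.0479, 0.0476 and 0.0446 (protocol: 0.0477, 0.0477, 0.0444). The method is therefore identified, and the plan's figures follow from it.

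**2. Margin.** Expected survivors are 149 x 0.35 = 52.15. The difference 98% vs 88% sits at p = 0.05 when n = 1.96² x 2 x 0.93 x 0.07 / 0.10² = 50.0. At 51 per arm p = 0.0478; at 50 it is just above 0.05. The tolerable loss is 1 - 50 / 52.15 = 4.1%.

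**3. Loss among survivors, any definition of long-term.**

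| Assumed loss | Survivors per arm | p for 98% vs 88% | Smallest significant difference from 98% |
|---|---|---|---|
| 0% | 52.15 (52) | 0.0457 | 9.7 points |
| 10% | 46.9 (47) | 0.0574 | 10.5 points |
| 20% | 41.7 (42) | 0.0725 | 11.4 points |
| 30% | 36.5 (37) | 0.0918 | 12.6 points |

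The last two columns use the rounded count.

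**4. Follow-up under the age cap.** Maximum follow-up = min(12, 25 - age at transplant): 12 years at exactly 13, 11 at 14, 10 at 15, 9 at 16, 8 at 17, and about 7 just under 18. Apart from the exact boundary at 13, nobody in the 13-17 band can complete 12 years, and everybody in it can complete 7.

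**5. Conditional on long-term survivor meaning observed for 12 years, and 35% being a 12-year rate.** With equal bands, 52.15 x 0.75 = 39.1 per arm, before any loss. At 39, 98% vs 88% gives p = 0.0835 and the smallest significant difference is 12.1 points; exactly 12 points (98% vs 86%) gives p = 0.0508. Normal-approximation power for 98% vs 88% falls from about 52% at 52 to about 41% at 39. For a 13-17 share of 10% to 30%, 46.9 to 36.5 remain. If long-term means 7 years or less, the factor is 1 and 52.15 stands.

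**6. Analysis.** By step 4, survivors differ in observation time by up to five years according to age alone. Logistic regression on incidence in Section 9.7.2.2.3 has no term for time observed. The Cox and Kaplan-Meier analyses in the same section do account for it.

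**The case against.** The strongest reply is that 149 has not been shown to be wrong. A reader might infer from steps 4 and 5 that the plan delivers 39 long-term survivors instead of 52, or that it must enrol 52 / (0.35 x 0.75), that is 199, per arm. The documents do not support this. Section 9.5 asks for long-term survivors, not twelve-year survivors, and lists 13-17 years among the age groups of those survivors. Twelve years is mostly written as a ceiling (Sections 6, 7.2 and 9.2.1). Section 7.2 places the gap in knowledge beyond 3 years, which an adolescent followed for 7 to 12 years helps to fill. Nothing removes patients who reach 25 from the comparison, and Section 9.5 says that all enrolled patients contribute. This objection stands, and the 39 is conditional only.

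It can also be said that covariate adjustment and propensity-score weighting are planned, and that censoring rules belong in a statistical analysis plan, which is not shown. Adjustment can reduce bias from a different age mix. It does not give an ever-observed proportion a definite time, and the choice of logistic regression for incidence endpoints is made in the protocol itself.

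The omission of age 25 from the study-end sentence is minor, because the same paragraph caps each patient's follow-up. It is still an inconsistency in the text. Nothing in the objection answers the missing allowance for loss and withdrawal.

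**Conclusion.** The point holds in limited form. The division 52 / 0.35 = 149 is correct as arithmetic, but it covers death only and leaves 52.15 expected survivors against a threshold of 50. About 4% loss or withdrawal among survivors is enough to undo the stated 10-point detectability. This does not depend on how long-term is defined, only on the pooled z-test that reproduces the protocol's table; the 47 to 37 range rests on the assumed 10% to 30% loss.

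The effect of the age cap on the count runs from nothing (7 years or less) to about a quarter (12 years observed, equal bands: about 39 per arm, just over 12 points). Equal bands are an aim, not a guarantee. The document does not say which reading applies.

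Independently of the count, the cap makes follow-up unequal by age, and the logistic comparison of incidence ignores that. It biases the treatment contrast to the extent that age at transplant differs between arms.

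**What to change.** 1. In Section 9.7.2.2.3, compare incidence endpoints with the Cox and Kaplan-Meier methods already planned, at fixed times that every age band can reach (no later than 7 years), with reaching age 25 treated as administrative censoring. This replaces logistic regression on crude proportions.
2. In Section 9.5, state the time point that defines a long-term survivor and the time point of the 35% rate. Restate the detectable difference for the survivors expected after a stated allowance for loss and withdrawal and, if 12 years is meant, after the age-25 exit as well: about 39 per arm and just over 12 points before loss. The 12-point figure in the protocol's table belongs to 40 per arm and does not reach p < 0.05 at 39.
3. Reconcile the study-end sentences in the Abstract and Section 9.2.1 with the age-25 exit.

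The cost is a less favourable stated figure and small wording changes. No additional patients or new methods are needed.

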This study (Study 20180130) will provide the opportunity to investigate the long-term safety profile in paediatric patients with respect to known short-term toxicities of blinatumomab, eg, those related to the immune, neurologic, and HSCT-related events. The study will involve long-term follow-up of both chemotherapy- and blinatumomab-treated paediatric patients who then undergo alloHSCT. Patients who have undergone alloHSCT following treatment with either blinatumomab or standard of care (SOC) chemotherapy will be invited to participate in the 20180130 study.

Study 20180130 will provide the opportunity to investigate the long-term safety profile of blinatumomab, by providing 12 years of follow-up of patients treated with either blinatumomab or chemotherapy, followed by alloHSCT (follow-up commencing at transplantation). The study will investigate neuropsychomotor developmental impairment, endocrine impairment, neurological impairment, and immune system impairment.

- Research Question and Objective(s)
 - Primary Objective

(1) To estimate incidence of neuropsychomotor developmental impairment, endocrine impairment, neurological impairment, and immune system impairment (including auto-immune disorders and vaccine failure)

- Secondary Objectives
 - (1) To estimate the incidence of HSCT related adverse events (AEs)
 - (2) To estimate the incidence of subsequent relapse of leukemia including in the CNS
 - (3) To estimate the cumulative incidence of long-term AEs
 - (4) To estimate the incidence of secondary malignant formation
 - (5) To estimate overall survival
- Hypothesis Estimation
 - The study will compare blinatumomab therapy versus chemotherapy treatment

for the occurrence of neuropsychomotor developmental impairment, neurological impairment, endocrine impairment, and immune system impairment.

• Study Design/Type

This study is a prospective observational study.

• Study Population or Data Resource

Paediatric patients who have undergone alloHSCT following treatment with either blinatumomab or SOC chemotherapy will be invited to participate in the study.

• Summary of Patient Eligibility Criteria

Inclusion Criteria

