 Hypothalamus-Pituitary-Adrenal (HPA) Axis disorders,
 Hypothalamus-Pituitary-GH Axis disorders,
 Hypothalamus-Pituitary-Thyroid Axis disorders
- Immune system impairment defined as any leukopenia (neutropenia and/or lymphopenia); low IgG; low IgM, and; low IgA; autoimmune disorders; vaccination failure

HSCT-related AE defined as any second malignancy; Graft versus Host Disease (GvHD); infection, and/or; relapse

Relapse is defined as any of the following:

- Isolated bone marrow relapse (M3¹ in the absence of extramedullary involvement)
- Combined bone marrow response (M2 or M3 marrow and at any extramedullary manifestation of ALL)
- Extramedullary relapse (either CNS relapse, testicular relapse, or relapse at other sites²)

AE in any of the following organ systems: gastrointestinal, hematologic, dermatology, cardiac, pulmonary, hepatic, renal, neurological, infection, immunology, and skeletal

Secondary malignancy: tumor type and anatomical site of tumor

Overall survival as time from transplant until death

¹ Cytological bone marrow assessment grading: see Appendix F for details

² See appendix F for relapse criteria (including extramedullary relapse)

Covariates

Demographics and clinical characteristics including comorbidity Recording of ALL-related diagnoses history both prior to and following blinatumomab/SOC chemotherapy

- Disease status (prior to blinatumomab/SOC chemotherapy)
- Minimal residual disease (MRD) status (following treatment);
 MRD positivity defined at a level ≥ 10⁻⁴ in polymerase chain reaction (PCR) and/or flow quantification
- Relapse (following treatment)
 - Time point of relapse (time since primary diagnosis and time after completion of primary therapy)
 - Whether extramedullary relapse
 - Bone marrow status at relapse
- Secondary malignancy (following treatment)

Recording of ALL-related treatment history

- Details of SOC-chemotherapy therapy: specific therapy, and; duration of therapy
- Details of blinatumomab therapy: number of cycles; occurrence of further blinatumomab therapy following initial discontinuation, and; duration of therapy

Recording of alloHSCT status

- Occurrence of alloHSCT(s)
 - Interval between SOC-chemotherapy/blinatumomab and alloHSCT

Clinically relevant events prior to initiation of SOC/blinatumomab therapy or after initiation of therapy and before alloHSCT

- Neurologic event
- Endocrine event (including evidence of growth delay)
- Immune event

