9.2.3 Patient Eligibility

9.2.3.1 Inclusion Criteria

Patients are eligible to be included in the study if they meet all of the following inclusion criteria.

- Paediatric B-cell precursor ALL patients with any indication world-wide that received blinatumomab or chemotherapy in routine clinical practice, followed by transplantation, or EU paediatric indications that may be authorized in the future. This means that paediatric patients which receive blinatumomab off-label in the EU or with a different indication in ex-EU regions may be included in the study.
- Patient's legally acceptable representative has provided informed consent when the patient is legally too young to provide informed consent and the patient has provided written assent based on local regulations and/or guidelines prior to any study-specific activities/procedures being initiated.

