9.6 Data Management

All data will be entered by sites into an eCRF that will be used to build the study database. Data abstraction will be done approximately every 6 months $(\pm 30 \text{ days})$ starting from enrolment. Additional data on neuropsychomotor development will be assessed through specific questionnaires (paper and/or electronic) which will be administered at pre-specified intervals starting at enrolment (approximately every 6 months [± 30 days] for patients up to 6 years old and approximately yearly [± 60 days] for patients from 6 years old) either in person or via telephone interview or mail. The score and percentiles from the questionnaires will be used for the final analysis. The final analysis cohort will be constructed from the complete review of inputted data documenting events in a patient's history from primary disease diagnosis until the earliest occurrence of the following events: death, withdrawal of consent, end of available data in the chart, completion of the 12-year follow-up period, or up to the age of 25 years. Data to be abstracted include variables relating to ALL diagnosis, ALL-associated treatment, development impairment, HSCT-associated AEs, leukemia relapse, long-term AEs, secondary malignancy until the earliest of: death, withdrawal of consent, end of available data in the chart, completion of the 12-year follow-up period, or 25 years of age.

Each patient will be assigned a unique identification number at the time of the first data entry. This unique identification number will be used to link data to subsequent data entries. The data will be abstracted by site staff from patient medical records into a web-based electronic data capture (EDC) system, using an electronic abstraction form that will provide an integrated, transparent tool to facilitate and record center recruitment, case identification, patient selection and study progress at the center and patient level.

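### Survival is timed from alloHSCT but patients enrol only afterwards, with no limit on the gap, so overall survival analysed without delayed entry is overstated

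*Protocol*

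**What the plan says.** Section 9.2.1 fixes the time origin: "The first day of follow-up (day 1) will be the date of successful completion of alloHSCT". The outcome variables in the Abstract define the survival endpoint to match: "Overall survival as time from transplant until death".

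Entry comes later. The Abstract says: "Patients who have undergone alloHSCT following treatment with either blinatumomab or standard of care (SOC) chemotherapy will be invited to participate". Under Section 9.2.1, enrolment through the interactive response system follows consent and confirmation of eligibility, and study data collection begins then.

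Nothing limits the time between transplant and enrolment. The clinical inclusion criterion in Section 9.2.3.1 asks only for "Paediatric B-cell precursor ALL patients with any indication world-wide that received blinatumomab or chemotherapy in routine clinical practice, followed by transplantation" (or a future EU paediatric indication). The other criterion is consent, and Section 9.2.3.2 lists no exclusions.

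Two provisions govern what is observed before enrolment. Questionnaires are "administered at pre-specified intervals starting at enrolment". Chart history, by contrast, reaches back: under Section 9.6 the analysis cohort is built from events "from primary disease diagnosis until the earliest occurrence of the following events: death, withdrawal of consent", or other end of follow-up.

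Sections 9.7.2 and 9.7.2.2.3 name Kaplan-Meier and Cox regression for time-to-event endpoints. They do not say when a patient enters the risk set. Section 9.9 discusses bias from non-consent, but not selection by survival to enrolment.

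**The concern.** A patient enrolled two years after transplant contributes two years in which death could not have been recorded, because dying would have prevented enrolment. If that patient is counted at risk from day 1, the denominators in those years contain people who could not die, while those who did die are absent. Estimated OS is too high.

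If the gap differs between arms, the arm with the longer gap gains more immortal time and its survival looks better, so the hazard ratio is biased even when the treatments do not differ. This is a post-authorisation safety study (Section 7.2), and OS is one of its secondary objectives.

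The non-fatal endpoints have a related, weaker problem. Early relapse, graft-versus-host disease or infection that proved fatal before enrolment is missing from the cohort.

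**Working it through.** **The plan's own figure.** Section 9.5 needs 52 long-term survivors per arm and assumes 35% long-term survival. 52 / 0.35 = 148.6, rounded up to 149 per arm, and 2 × 149 = 298. This reproduces exactly.

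**Inputs.** From the protocol: survival of 35% (Section 9.5), taken here as 12-year OS from transplant, and a maximum follow-up of 12 years (Section 9.2.1). Assumed, because the protocol does not give them: the gap g from alloHSCT to enrolment, and the shape of the survival curve.

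**Apparent OS.** If everyone enrols g years after transplant and is counted at risk from day 1, the estimate at 12 years is S(12) / S(g) instead of S(12). Three shapes were tried:

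- Constant hazard: S(12)/S(g) = 0.35^(1 − g/12). For g = 1: 0.35^0.917 = 0.382.
- Early deaths, Weibull shape 0.5: S(12)/S(g) = 0.35^(1 − √(g/12)). For g = 1: 0.35^0.711 = 0.474.
- Early deaths falling to a plateau: S(t) = 0.35 + 0.65·exp(−t/2), so S(12) = 0.352. For g = 1: 0.352 / 0.744 = 0.472.

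| Gap (years) | Constant hazard | Weibull 0.5 | Plateau |
|---|---|---|---|
| 0.5 | 36.6% | 43.4% | 41.1% |
| 1 | 38.2% | 47.4% | 47.2% |
| 2 | 41.7% | 53.7% | 59.7% |

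The true value is 35% in every row.

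**Hazard ratio.** Survival times were simulated with a true hazard ratio of 1 and 20,000 patients per arm, and Cox models were fitted with and without delayed entry. The ratio is blinatumomab to chemotherapy, and the gaps are assumed.

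| Gap, blinatumomab / chemotherapy (years) | Constant hazard: no delayed entry | Constant hazard: delayed entry | Weibull 0.5: no delayed entry | Weibull 0.5: delayed entry |
|---|---|---|---|---|
| 0.5 / 0.5 | 0.99 | 0.99 | 1.01 | 1.01 |
| 0.5 / 2 | 1.22 | 0.98 | 1.50 | 1.01 |
| 0.5 / 3 | 1.43 | 1.00 | 1.84 | 1.02 |

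Reversing the gaps inverts the bias: 1/1.43 = 0.70 and 1/1.84 = 0.54 for the last row.

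**Effect on study size.** If the 35% runs from transplant and all patients enrol at one year, the number needed for 52 survivors is 52 / 0.382, rounded up to 137 per arm (constant hazard), or 52 / 0.474, rounded up to 110 (Weibull 0.5). Both are below 149.

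**The case against.** The strongest reply is that the protocol does not state the error. It fixes an origin and names two methods, and both accept delayed entry. A reader might infer that the plan places patients in the risk set from day 1. It does not say so, and a separate analysis plan, not at hand, may set the entry rule. This stands as a limit on the wording. It does not remove the point, because the transplant origin and the open-ended entry are both fixed in the protocol and together make such a rule necessary.

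A reader might also infer that every time-to-event result carries immortal time. Section 9.6 does not support that: chart review reaches back to diagnosis, so recorded non-fatal events before enrolment can be captured. The interval is strictly event-free only for death. The exception in the other direction is questionnaire-based impairment, which cannot be seen before the first questionnaire.

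For the same reason, delayed entry in every first-onset analysis would be a poor remedy. It would remove patients whose first event is already charted, and Section 9.5 expects 85% to 98% of patients to have at least one event.

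Multi-year gaps are not established either. The study is prospective, and Section 9.7.1 speaks of allowing time to accrue treated patients, which suggests enrolment near transplant. Nor does any section say that chemotherapy patients were transplanted longer ago. Against this, Section 7.1.3 dates US approval including children to 2014 and Section 6 starts data collection in about Q2 2020, so transplants well in the past could qualify in either arm.

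**Conclusion.** The point holds for OS: the interval from alloHSCT to enrolment is immortal, and analysis from transplant without delayed entry overstates survival. With true 12-year OS of 35% and gaps of 0.5 to 2 years, the overstatement is about 2 to 7 percentage points at constant hazard and about 6 to 25 with early deaths. These sizes rest on assumed gaps and curves. If enrolment follows transplant closely, the bias is small.

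Bias in the hazard ratio needs unequal gaps. Its direction is unknown, and with equal, short gaps the ratio stays near 1. Other endpoints are conditional on survival to enrolment and miss early fatal relapse, graft-versus-host disease and infection.

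A reader might infer that the 298 is wrong. The documents do not support that: the arithmetic is right, and better survival after enrolment would yield more than the 52 survivors sought. What is unclear is only whether the 35% is counted from transplant or from enrolment.

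**What to change.** - **OS:** keep alloHSCT as time origin, but enter each patient into the risk set at the enrolment date, in both the Kaplan-Meier and the Cox analysis.
- **Non-fatal first-onset endpoints:** keep the chart-captured events before enrolment. State that the estimates are conditional on survival to enrolment, and that questionnaire-based impairment is observed only from enrolment. Add a sensitivity analysis limited to patients enrolled within a fixed short window after alloHSCT.
- **Reporting:** tabulate the gap from alloHSCT to enrolment by arm.
- **Section 9.5:** state whether the 35% survival rate runs from transplant or from enrolment.

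No new data are needed, since the transplant and enrolment dates are already held. The cost is smaller early risk sets and less precise early OS estimates. If few patients enrol soon after transplant, the first part of the curve will be poorly supported and should be reported as such. Delayed entry also assumes that, given the covariates, the time of enrolment is unrelated to prognosis.
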